8.2 Demographic and Baseline Characteristics

No formal comparison between treatment groups on demographic and baseline characteristics will be performed.

8.2.1 Demographic and Baseline Characteristics

Demographic and baseline characteristics will be summarized by treatment group and overall using descriptive statistics for ITT Set. These will include age, age category, gender, and childbearing potential or not, race, height, weight at baseline and body mass index (BMI) at baseline.

Notes:

- BMI will be calculated as: weight (kg) / height (m²).
- Age categories are: 18-64 (years); 65 + (years). All categories must be reported even if there are no subjects under a particular category.

An individual subject listing will also be provided for demographic and baseline characteristics data.

8.2.2 SAS COVID-19 ARDS History

Days between screening positive SARS-COV-19 rt-PCR test and start of intubation, days between ICU admission date and start of intubation, and SARS COVID-19 ARDS medication categories recorded at Screening Visit will be presented by treatment group and overall for Safety Set.

In addition, SAS COVID-19 ARDS history data will be presented in an individual listing.

Notes:

- Days between screening positive SARS-COV-19 rt-PCR test and start of intubation = Start date of intubation – Date of screening positive SARS-COV-19 rt-PCR test + 1.
- For subject with intubation done after ICU admission: Days between ICU admission date and start of intubation = Start date of intubation – Date of ICU admission + 1.
- For subject with intubation done before ICU admission (transfer from another hospital): Days between ICU admission date and start of intubation = Start date of intubation – Date of ICU admission.

8.2.3 Other Baseline and Disease Characteristics

The following baseline and disease characteristics parameters will be summarised using descriptive statistics by treatment group and overall based on ITT Set:

- Vital signs (systolic blood pressure (SBP), diastolic blood pressure (DBP), and pulse rate) at baseline;
- Ventilatory parameters at baseline (PaO₂/FiO₂ ratio and FiO₂);
- SOFA score at baseline.

8.3 Medical History and Concomitant Diseases

Medical/surgical history and concomitant diseases will be summarized by System Organ Class (SOC) and Preferred Term (PT), by treatment group and overall, using Safety Set.

Notes:

- Medical/surgical history is defined as conditions in the medical/surgical history and concomitant diseases eCRF form which are not ongoing at Screening (even if end date is missing);
- Concomitant diseases are defined as conditions in the medical/surgical history and concomitant diseases eCRF form which are ongoing at Screening.

In addition, medical, surgical and concomitant diseases data will be listed.

8.4 Medications

Prior medications, medications maintained during the treatment period, and concomitant medications will be summarized by treatment group, using Safety Set through frequency

distributions and percentages by Anatomical Main Group [1st level of the Anatomical Therapeutic Chemical (ATC) classification], Therapeutic Subgroup (2nd level of the ATC classification), Chemical Subgroup (4th level of the ATC classification) and Preferred Name.

The medications will be classified according to the following rules:

- For poractant alfa group:
 - Prior medication: start date < date of first study medication administration and stop date \leq date of first study medication administration;
 - Medication maintained during the treatment period: start date < date of first study medication administration and stop date $>$ date of first study medication administration or ongoing;
 - Concomitant medication: start date \geq date of first study medication administration.
- For control group:
 - Prior medication: start date < start date of randomization and stop date \leq start date of randomisation;
 - Medication maintained during the treatment period: start date < start date of randomisation and stop date $>$ start date of randomisation or ongoing;
 - Concomitant medication: start date \geq start date of randomisation.

8.5 Procedures

Prior procedures, procedures maintained during the treatment period and concomitant procedures will be summarized (including intubation) by treatment group, using Safety Set through frequency distributions and percentages by SOC and PT.

The procedures will be classified according to the following rules:

- For poractant alfa group:
 - Prior procedure: start date/time (if time is available) < date/time of first study medication administration and stop date/time (if time is available) \leq date/time of first study medication administration;
 - Procedure maintained during the treatment period: start date/time (if time is available) < date/time of first study medication administration and stop date/time (if time is available) $>$ date/time of first study medication administration or ongoing;
 - Concomitant procedure: start date/time (if time is available) \geq date/time of first study medication administration.
- For control group:
 - Prior procedure: start date/time (if time is available) < start date/time of randomization and stop date/time (if time is available) \leq start date/time of randomization;

- Procedure maintained during the treatment period: start date/time (if time is available) < start date/time of randomization and stop date/time (if time is available) > start date/time of randomization or ongoing;
- Concomitant procedure: start date/time (if time is available) \geq start date/time of randomization.

8.6 Compliance

Not Applicable.

9 Efficacy Analyses

All the efficacy comparisons between the treatment groups will be based on the ITT Set.

9.1 Primary Efficacy Variable

The primary efficacy variable is the number of days alive and ventilator-free days, defined as the number of days the subject is not receiving mechanical ventilation over the 21 days following randomization. Mechanical ventilation is defined as invasive and non-invasive. Subject is defined free of mechanical ventilation after 12 hours from the suspension of either invasive or non-invasive ventilation.

Subjects who die or are mechanically ventilated longer than this period are assessed as zero ventilator-free days.

Notes:

Subjects with at least 12 hours of suspension of ventilation either invasive or non-invasive ventilation will be flagged. Then duration will be calculated within the flagged subject's subset, as below:

- Ventilator-free days = 21-[MAX (End date of invasive ventilation; End date of non-invasive ventilation)] – Date of randomisation + 1.

Descriptive summaries of the number of ventilator-free days will be presented by treatment group.

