4.2 Inclusion Criteria

Participants are eligible to be included in the study if the following criteria apply:

1. Male or female ≥ 18 and ≤ 80 years of age
2. Informed consent for participation in the study (*refer to [section 15](#) for detailed informed consent procedure*)
3. Positive SARS-COV-19 rt-PCR before randomisation
4. PaO₂/FiO₂ ratio < 150 mmHg
5. Lung compliance ≤ 45 ml/cmH₂O
6. Intubated and artificially ventilated less than 48 hours before the first poractant alfa administration

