In case the patient will be assigned to the poractant alfa treated group, the treatment must start soon after the randomization (max 2 hr), and within 48hr after intubation

The following procedures for treated group or for control group will be conducted according to the frequencies reported in the above flowchart:

- Treatment procedure for poractant alfa as described in detail in [section 6.2](#). One administration per day with a 24 hours interval
- Arterial Blood Gas (ABG) Analysis
- Ventilatory support
- Ventilatory parameters: PaO₂/FiO₂, FiO₂, tidal volume (TV), respiratory rate (RR), static compliance (Cstat), dynamic compliance (Cdyn), PEEP (positive end-expiratory pressure), PIP (peak inspiratory pressure), Plateau Pressure (Pplat)
- Laboratory assessments for mechanistic analysis: blood sampling and bronchial washings; bronchoscopic washings performed as clinically indicated only, with surplus samples retrieved for mechanistic study as available (for more details ref. to [section 7.2](#))

Clinical Study Code No.: CLI-050000-04	Version No.: 4.0
EUDRACT No.: 2020-002632-75 – IND No: 153286	Date: 02 MAR 2021

- Laboratory assessments: blood count, bilirubin, creatinine, eGFR, LDH, D-dimer, CRP, procalcitonin
- Vital signs will be obtained as appropriate
- SOFA score is calculated considering PaO₂/FiO₂, Glasgow coma scale, mean arterial pressure, and bilirubin, platelet and creatinine levels
- AEs review (including SAEs)
- Concomitant medications and procedure review as applicable

7.1.3 Day 4 – 27 recording:

The following procedures for treated group or for control group will be conducted according to the above flowchart

- Arterial Blood Gas (ABG) Analysis
- Ventilatory support: extubation date recorded (as applicable) and following ventilation procedures recorded
- Ventilatory parameters: PaO₂/FiO₂, FiO₂, tidal volume (TV), respiratory rate (RR), static compliance (Cstat), dynamic compliance (Cdyn), PEEP (positive end-expiratory pressure), PIP (peak inspiratory pressure), Plateau Pressure (Pplat)
- Vital signs will be obtained as appropriate
- AEs review (including SAEs)
- Concomitant medications and procedure review as applicable
- Discharge date from ICU if applicable

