4.1 Efficacy Variables

4.1.1 Primary Efficacy Variable

The primary efficacy variable is the number of days alive and ventilator-free defined as the number of days the subjects is alive and not receiving mechanical ventilation over the **21 days** following randomisation.

Mechanical ventilation is defined as invasive and non-invasive. Subject is defined as free of mechanical ventilation after 12 hours from the suspension of either invasive or non-invasive ventilation. Subjects who die or are mechanically ventilated longer than this period are assessed as zero ventilator-free days.

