9.3 Others Secondary Efficacy Variables

9.3.1 Number of Days Alive and Ventilator-free at Day 28

First, within subject with a start date filled in the ventilator support form, subjects with at least 12 hours of suspension of ventilation either invasive or non-invasive ventilation will be flagged. Then duration will be calculated within the flagged subject's subset, as below:

- Ventilator-free days = 28-[MAX (End date of invasive ventilation; End date of non-invasive ventilation)] – Date of randomisation + 1].

Subjects who die or are mechanically ventilated longer than this period are assessed as zero ventilator-free days.

Number of ventilator-free days will be described at Day 28.

9.3.2 Mortality at Day 21 and Day 28

The number and proportion of deaths at Day 21 and Day 28 will be presented for both groups.

9.3.3 Number of Days Alive and Free from invasive and Non-Invasive ventilation at Day 21 and Day 28

For Day 21:

First, subjects with at least 12 hours of suspension of ventilation will be flagged by type (i.e. one flag for Non-Invasive, and one for Invasive). Then duration will be calculated within the flagged subject's subsets, as below:

- Invasive ventilation-free days = 21-(End date of invasive ventilation) – Date of randomisation + 1].
- Non-invasive ventilation-free days = 21-(End date of non-invasive ventilation) – Date of randomisation + 1].

If subject never started a non-invasive ventilation then the value will be set to 21 days.

For Day 28:

First, subjects with at least 12 hours of suspension of ventilation will be flagged by type (i.e. one flag for Non-Invasive, and one for Invasive). Then duration will be calculated within the flagged subject's subsets, as below:

- Invasive ventilation-free days = 28-(End date of invasive ventilation) – Date of randomisation + 1].

- Non-invasive ventilation-free days = 28-(End date of non-invasive ventilation) – Date of randomisation + 1].

If subject never started a non-invasive then the value will be set to 28 days.

Subjects who die or are mechanically ventilated longer than this period are assessed as zero ventilator-free days.

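### The SAP derivations of ventilator-free days, NIV-free days and ICU stay do not return the stated endpoints for re-ventilated survivors, NIV users and deaths after ICU discharge

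*SAP*

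**What the plan says.** **Ventilator-free days.** SAP 4.1.1 defines the primary variable as the "number of days the subjects is alive and not receiving mechanical ventilation over the" 21 days after randomisation. Invasive and non-invasive ventilation both count, and a subject is free once 12 hours have passed off either. SAP 9.1 computes it as "Ventilator-free days = 21-[MAX (End date of invasive ventilation; End date of non-invasive ventilation)] – Date of randomisation + 1". SAP 9.3.1 repeats this for Day 28: "Ventilator-free days = 28-[MAX (End date of invasive ventilation; End date of non-invasive ventilation)] – Date of randomisation + 1". A zero rule goes with both: "Subjects who die or are mechanically ventilated longer than this period are assessed as zero ventilator-free days".

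**NIV-free days.** SAP 9.3.3 uses "Non-invasive ventilation-free days = 21-(End date of non-invasive ventilation) – Date of randomisation + 1" for subjects who had NIV. For the others, "If subject never started a non-invasive ventilation then the value will be set to 21 days", with 28 in the Day 28 version. The zero rule closes the section, and the footnote to Table 14.2.6 repeats it.

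**ICU stay.** Protocol section 8 and SAP 9.3.8 assign 28 days to subjects who die. SAP 9.3.8 identifies them by a death date earlier than the minimum of the ICU discharge date and the Day 28 date.

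**The concern.** The endpoint text describes a count of days. The derivations use a single date and ignore what happened before it. They also do not stop at the end of the window.

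The trial expects the courses for which this matters. Every patient enters on invasive ventilation ("Intubated and artificially ventilated less than 48 hours before the first poractant alfa administration"). Protocol 7.1.3 has the "extubation date recorded (as applicable) and following ventilation procedures recorded". SAP 9.3.8 provides for several invasive sessions and for ICU readmission. NIV after extubation is itself an endpoint.

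At stake are the reported values of the primary variable and several secondary ones. SAP 7.5 and section 12 reduce all efficacy analysis to description, so these summaries are the efficacy result. The trial closed below its target of 70, so each wrong value weighs more than planned.

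**Working it through.** **Inputs.** Randomisation is Day 1 (SAP 7.9.3). Windows W are 21 and 28. Planned arms are 42 and 28, with a planned difference of 4 days and SD 5.5 (SAP section 5). The patient courses are illustrative, in whole calendar days.

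**The plan's own figure.** 4 / (5.5 × √(1/28 + 1/42)) = 2.98, which gives 83.6% power by noncentral t and 84.6% by normal approximation. The stated 84% reproduces and is not affected by this point.

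**Reading of the formula.** I take it as W − (last end date − randomisation date + 1), that is, W minus the day number of the last end date. The printed brackets do not group this way in 9.1 and do not balance in 9.3. That may come from the PDF conversion, and nothing here rests on it.

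**Ventilator-free days, survivors**

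| Days ventilated | W | Count of days off | Formula |
|---|---|---|---|
| 1-17 | 21 | 21 − 17 = 4 | 21 − 17 = 4 |
| 1-5 and 18 | 21 | 21 − 6 = 15 | 21 − 18 = 3 |
| 1-5 and 18 | 28 | 28 − 6 = 22 | 28 − 18 = 10 |
| 1-5 and 19-20 | 21 | 21 − 7 = 14 | 21 − 20 = 1 |
| 1-6 and 23-26 | 21 | 21 − 6 = 15 | 21 − 26 = −5 |

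A single spell is handled correctly. With a second episode, days off between episodes are lost. The fourth course has 14 days off but scores 1, below the first course, which has 4.

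In the last course the second episode lies wholly outside the 21-day window. The result depends on the zero rule. SAP 9.3.8 and the footnote to Listing 16.2.6.1 measure duration from first start to last end. That span is at least 26 days here, which exceeds 21, so the value is 0 and the error is 15 days. If the zero rule is not applied this way, the value is −5 and the error is 20 days.

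Shift in an arm mean from one such patient: 15/42 = 0.36 and 15/28 = 0.54 days; with the larger error, 20/42 = 0.48 and 20/28 = 0.71 days.

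The invasive-free formulas in 9.3.3 are built the same way and share the fault.

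**NIV-free days.** Patient A: invasive Days 1-5, NIV Days 6-7. Patient B: invasive Days 1-5, never NIV.

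| Meaning of NIV-free | A, W=21 | B, W=21 | A, W=28 | B, W=28 |
|---|---|---|---|---|
| Days without NIV | 19 | 21 | 26 | 28 |
| Days free of both types | 14 | 16 | 21 | 23 |
| Days after last NIV ended | 14 | 21 | 21 | 28 |
| SAP 9.3.3 | 14 | 21 | 21 | 28 |

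Two days of NIV cost seven days. The SAP values match only the third meaning, which no section states.

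**ICU stay.** Discharge Day 10, death Day 14. The test asks whether 14 < MIN(10, 28) = 10. It is not, so the computed stay stands: 10 days for ICU entry on Day 1, 12 for entry 2 days before randomisation, 17 for 7 days before (entry dates assumed). The stated rule gives 28.

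**The case against.** - **Last liberation may be the intended convention.** SAP 9.3.8 and Listing 16.2.6.1 also collapse sessions to the last end date, and on that reading 3 and 1 are the right scores. This is possible, but neither document says it and 4.1.1 says otherwise. It does not rescue the last course: last liberation capped at Day 21 gives 15.
- **Negative primary values.** A reader might infer that the primary table will contain them and that 20 days is the size of the error. The documents do not support that firmly. Any negative value needs a last end date after Day 21 in a patient ventilated from entry, and the overall-span calculation would set it to 0. The range is 15 to 20 days and turns on an ambiguous clause.
- **The counts are not fully determined.** The 12-hour rule is only a flag in 9.1, and whether those hours count is not stated. The 15s and 14s are whole-day counts. Moving them by a day would not close a gap of 12 days.
- **NIV.** A reader might infer that one branch must be wrong on any reading, or that nothing says whether the zero rule beats the 21/28 default. Neither holds: the branches agree under last NIV liberation, and the Table 14.2.6 footnote shows that the zero rule is meant to apply. What stands is that the convention is unstated and 9.3.3 does not spell out the order.
- **ICU clock.** Counting from ICU entrance lets a survivor exceed 28 days. That is an inconsistency of scale, not a miscalculation.
- **Limited effect.** No test or model uses these values, and the listings show episode dates and derived values. This lowers the rating but does not make the derivations right.

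**Conclusion.** The derivations are wrong as written and should be fixed. For survivors with more than one ventilation episode, the primary variable departs from its definition: by 12 or 13 days in the courses with re-ventilation inside the window, and by 15 to 20 days where it starts after Day 21. NIV-free days follow a convention that the SAP does not state. The ICU death test contradicts the rule it is meant to carry out.

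This rests on the 4.1.1 definition meaning what it says, on whole-day counting, and on the favourable reading of the brackets. The courses are constructed, and the frequency of re-ventilation, NIV use and death after ICU discharge is not given, so the net effect on either arm cannot be stated. A reader might infer that a primary hypothesis test is compromised. It is not, because the SAP plans no efficacy test.

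**What to change.** 1. **Ventilator-free and invasive-free days (SAP 9.1, 9.3.1, 9.3.3).** For subjects not set to zero, sum the ventilation-free days within Days 1-21 (1-28) from episode start and stop date/times, truncating episodes at the window end and applying the 12-hour rule. Say whether the first 12 hours off count. State that the zero rule refers to status within the window, not to a span that includes later episodes. If last liberation is intended, say so in 4.1.1, count only episodes that start on or before Day W, and use max(0, W − (MIN(last end date, Day W) − randomisation date + 1)). Write the formulas with balanced brackets.
2. **NIV-free days (9.3.3).** Count from NIV episode dates within the window, state whether days on invasive ventilation count as NIV-free, and say that the zero rule overrides the 21/28 default.
3. **ICU stay (9.3.8).** Assign 28 to any death on or before Day 28, whatever the ICU discharge date. Capping the stay at 28 or counting from randomisation is optional; the latter would be a change of definition and must be declared.

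The cost is derivation wording and code. Episode date/times are in Listing 16.2.6.1, and ICU and death dates are already used in 9.3.8. The SAP is final at version 1.0, so the changes can be explained in the clinical study report, as SAP section 1 provides.

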7.9.3 Study Day

If not otherwise specified, all assessment days will be related to date of randomization.

The randomization date is referred to as Day 1.

- If the date of the assessment is on or after the randomisation, then
Study Day = (date of assessment – randomisation date) + 1.
- If the date of the assessment is prior to the randomisation, then
Study Day = (date of assessment – randomisation date).

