Listing 16.2.6.1	Ventilatory Support (Intention-To-Treat Set)		
The following columns will be presented:
 
 - Subject ID - Randomized Treatment - Actual Treatment - Ventilator Type - Start Date/Time [Day] - Stop Date/Time [Day] or Ongoing - Duration of Ventilatory Support (Days) – displayed by Type of Support (Invasive or Not Invasive) - Overall Duration of Ventilator Support 	Add the footnotes: [1]: Duration of ventilatory support have been calculated as the difference between end date and start date +1. [2]: Overall duration of ventilatory support has been calculated as the difference between the maximum end date (between invasive and non-invasive ventilation) and start date +1.

Listing Number	Listing Title	Template Code	Notes	Footnotes
Listing 16.2.6.2-a	Ventilatory Parameters by Timepoint (Intention-To-Treat Set)	VSL002	
 - Remove 'Analysis Period' - Display 'Assessment date/Time [Study Day]' instead of 'Assessment date/time [study day / study day in period]' - Do not display [H] flag in Change from baseline column - Skip the last column (Change from pre-dose) - In Test <Unit> column, display: 
 - FiO2 (%) - Mean Arterial Pressure (mmHg) - Dynamic Compliance (ml/cmH₂O) - Static Compliance (ml/cmH₂O) - PaO₂/FiO₂ Ratio - Tidal Volume (ml/kg BW) - Respiratory Rate (/min) - Peak Inspiratory Pressure - PIP (cmH₂O) - Plateau Pressure (cmH₂O) - Positive End-Expiratory Pressure - PEEP (cmH₂O) - Blood Flows (L/min) - Sweep Gas Flows (L/min) - Add a last column displaying PaO₂/FiO₂ Ratio Improvement (<20%, >=20% or death) 	Add the footnotes: [1]: Baseline=Y flags baseline value [2]: Use=Y: included in the analysis [3] Duplicated data reported twice at 2 different timepoints are reported at the first occurrence for post dose/post randomisation and at the last occurrence for pre dose/pre randomisation.

Listing Number	Listing Title	Template Code	Notes	Footnotes

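### The ventilator-free-day formula in SAP 9.1 is bracketed so that it is not a day count; the rest of the SAP points to 20 − k, but a repair from 9.1 alone could give 2 days more

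*SAP*

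**What the plan says.** SAP 9.1 describes the endpoint as "defined as the number of days the subject is not receiving mechanical ventilation over the 21 days following randomization" and sets some patients to zero: "Subjects who die or are mechanically ventilated longer than this period are assessed as zero ventilator-free days". For the remaining patients the value comes from a formula:

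- **9.1 (Day 21, primary):** "Ventilator-free days = 21-[MAX (End date of invasive ventilation; End date of non-invasive ventilation)] – Date of randomisation + 1". The only square bracket closes straight after the MAX term.
- **9.3.1 (Day 28):** "Ventilator-free days = 28-[MAX (End date of invasive ventilation; End date of non-invasive ventilation)] – Date of randomisation + 1". Here the SAP prints one more closing square bracket after the last term, with no opening bracket to match it.
- **9.3.3 (invasive and non-invasive separately, Day 21 and Day 28):** four formulas of the type "Invasive ventilation-free days = 21-(End date of invasive ventilation) – Date of randomisation + 1", each again followed by an unmatched closing square bracket.

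Three other places bear on the intended grouping:

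- SAP 7.9.3: "The randomization date is referred to as Day 1", and for dates on or after randomisation "Study Day = (date of assessment – randomisation date) + 1".
- SAP 16.2, footnote to Listing 16.2.6.1: overall duration of support is "the difference between the maximum end date (between invasive and non-invasive ventilation) and start date +1".
- SAP 9.3.3: a patient who never started non-invasive ventilation scores 21 at Day 21 and 28 at Day 28.

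SAP 14 gives no code, and there is no worked example.

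**The concern.** A derivation rule for a primary endpoint should be programmable as printed. This one is not. In 9.1 both the end date and the randomisation date are subtracted from 21, so the programmer has to choose where the bracket was meant to close. The choice matters because the final + 1 changes sign depending on whether it falls inside or outside the bracket.

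The primary formula is also the only one of the six without the trailing bracket that shows the intended grouping. Someone working from 9.1 alone lacks the clue that 9.3.1 and 9.3.3 supply. The reported group means and medians of the primary endpoint are at stake, together with consistency between the Day 21 and Day 28 counts.

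The point concerns only the arithmetic of the formula. It does not concern which ventilation end date is used or how the 12-hour rule is applied.

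**Working it through.** **Inputs.** The six formulas are from SAP 9.1, 9.3.1 and 9.3.3, the day convention from 7.9.3, the zero rule from 9.1, and the sample size figures from SAP 5. R is the randomisation date, E the latest ventilation end date, and k = E − R. Calendar dates and shares of weaned survivors are my assumptions, because the documents give none.

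**1. The plan's own figure.** SAP 5 states 84% power for a 4-day difference with 42 and 28 patients, SD 5.5 and two-sided alpha 0.05. The noncentrality is 4 / (5.5 × √(1/42 + 1/28)) = 2.98 on 68 degrees of freedom, which gives 83.6% (normal approximation 84.6%). The figure reproduces and does not depend on the day-count formula.

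**2. Literal reading of 9.1.** 21 − E − R + 1 = 22 − E − R. SAS stores dates as days since 1 January 1960.
- R = 5 May 2021 (22405), E = 15 May 2021 (22415): 22 − 22415 − 22405 = −44,798.
- R = 1 April 2021 (22371), k = 10: 22 − 22381 − 22371 = −44,730.

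The same 10 days give different answers on different calendar dates, so this is not a day count.

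**3. Possible groupings for Day 21.**
- Bracket closes after + 1: 21 − [E − R + 1] = 20 − k.
- Bracket closes before + 1: 21 − [E − R] + 1 = 22 − k.
- Window starts the day after randomisation: 21 − k.

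| k | Study Day ventilation ended | 20 − k | 21 − k | 22 − k |
|---|---|---|---|---|
| 0 | 1 | 20 | 21 | 22 |
| 3 | 4 | 17 | 18 | 19 |
| 10 | 11 | 10 | 11 | 12 |
| 20 | 21 | 0 | 1 | 2 |

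Unbounded, the first and last groupings always differ by 2. Bounded to 0–21, the gap falls to 1 at k = 0 (20 vs 21). At k = 21 it is 1 (0 vs 1), or 0 if that patient counts as ventilated beyond the window.

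**4. Which grouping the SAP supports.** Under 7.9.3, E − R + 1 is the Study Day on which ventilation ended. Subtracting it from 21 leaves the days after that day up to and including Day 21, which is 20 − k. The listing footnote uses the same inclusive count. The stray closing bracket in all five formulas in 9.3 sits after + 1, where this grouping needs it. The 22 − k grouping would give a patient whose non-invasive ventilation ended on Day 1 a score of 22, above the 21 that 9.3.3 gives a patient who never had it.

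**5. Effect on the arms if 22 − k were used instead of 20 − k.** Patients at zero do not move. Each weaned survivor moves by 2 (ignoring bounds). An arm mean shifts by 2 × p, where p is its share of weaned survivors, and the arm difference by 2 × (p₁ − p₀).

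| Assumed p₁ vs p₀ | Shift in arm means (days) | Shift in difference (days) |
|---|---|---|
| 50% vs 50% | 1.0 and 1.0 | 0 |
| 60% vs 40% | 1.2 and 0.8 | 0.4 |
| 60% vs 30% | 1.2 and 0.6 | 0.6 |

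**The case against.** The strongest reply is that this is a slip of notation with a recoverable meaning. A reader might infer that the plan leaves two equally natural repairs open. The documents do not support that: the five formulas in 9.3, the Study Day rule and the listing footnote all favour 20 − k, and 22 − k can overrun its own window. This part of the objection stands.

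A reader might also infer that a nonsensical value could reach the results. That is unlikely. A count near −44,800 would be noticed at once, the listings print ventilation stop dates with study days next to the derived counts, and SAP 13.4 provides for a quality control plan. Nor do the documents show that Day 21 and Day 28 were programmed on different conventions. The brackets only make that possible.

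It is also tempting to set the shift against the planned 4-day effect. SAP 9.1, 7.5 and 12 replace the planned comparison with descriptive summaries, and Table 14.2.1 drops the confidence interval for the mean, so no test of that effect remains to be distorted. This also stands.

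Text extraction might have lost an opening bracket in 9.3.1 and 9.3.3. It would not explain 9.1, where the brackets balance but close in the wrong place.

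The objection does not remove the need for a correction. The primary formula cannot be run as printed, it alone lacks the trailing bracket, and no code or example in the SAP settles the matter.

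**Conclusion.** The formula in SAP 9.1 is wrong as written, and the five formulas in 9.3.1 and 9.3.3 are unbalanced. The supported reading is N − [end date − randomisation date + 1], which is 20 − k for Day 21 and 27 − k for Day 28. If 9.1 were repaired from its own text as 22 − k, each weaned survivor would score 2 days more, or less at the extremes if values are bounded to 0–21.

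The effect would be on reported group means or medians only. The arm difference in means would move by 0 to 0.6 day for assumed gaps of 0 to 30 points in the share of weaned survivors, and by nothing if the shares are equal. No test, confidence interval or the 84% power figure depends on it.

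One matter stays open. 9.1 speaks of the 21 days following randomisation, while 7.9.3 makes the randomisation date Day 1. If Day 1 is not meant to count within the window, the Day 21 value is 21 − k.

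**What to change.** - Print all six formulas (one in 9.1, one in 9.3.1, four in 9.3.3) as N − [end date − randomisation date + 1], with N = 21 or 28. In 9.1 and 9.3.1 the end date is the later of the invasive and non-invasive end dates.
- State that values are bounded to 0–N.
- Confirm in 9.1 that Day 1 counts within the 21-day window. If it does not, change the formula to match. Use the same convention for Day 21 and Day 28.
- Add one worked example: with Day 1 counted, ventilation ending on Day 11 gives 21 − 11 = 10 days.
- If outputs already exist, state in the clinical study report which convention was programmed and that it was the same at both time points.

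The cost is SAP wording in six formulas and a check of the derivation program. No new data are needed.
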